**Protocol Version History:**

*Original Protocol: Version 1, dated 02/14/2013*

*Protocol Amendment 1: Version 2, dated 04/07/2014*

*Protocol Amendment 2: Version 3, dated 05/01/2015*

**Précis /Abstract:**

The objective of this project is to accurately determine the constituents and characteristics of atherosclerotic plaques in carotid arteries by magnetic resonance imaging (MRI) techniques in cancer survivors; at different data intervals: before and after administration of treatment (medical and life style modification) and then correlate contrast agent dynamics with serum markers of inflammation and other tests of cardiac or vascular dysfunction where available.

The proposed study involves 100 asymptomatic patients who received prior chest or head and neck radiation therapy (HNXRT). MRI data (direct assessment of atherosclerosis) would be correlated with indirect measures of atherosclerosis (blood surrogate markers, metabolomics, Echocardiographic assessment and CT coronary calcium score).

Atherosclerosis is a chronic inflammatory process in the walls of arteries leading to plaque formation. Broadly, this process leads to stenosis of the arterial lumen by formation of atheromatous core (smooth muscle thickening, lipid accumulation such as cholesterol, lipid laden macrophages, calcium etc.) between the intimal layer and media layer of the arterial wall. Over the course of time, necrosis in these fat cells occurs, which leads to extracellular accumulation of lipids. At this stage, plaque is separated from the lumen of the vessel wall by a thin fibrous cap (FC) tissue and endothelial layer. Thin fibrous cap is a weak structure and is vulnerable to rupture resulting in either thrombus formation or a thromboembolic event.

Thrombus formation can lead to complete occlusion of an arterial lumen in spite of having mild or moderate stenosis. Besides ruptured plaque constituents might embolize (break away) and occlude a smaller downstream vessel leading to tissue damage. Research studies have demonstrated that necrotic lipid core with a thin fibrous cap presents a significant increased risk for plaque rupture resulting in a thromboembolism (1-6). Several scientific studies and publications have demonstrated that, of all etiologies of non-cancer mortality, cardiovascular disease (CVD) remains the most significant cause of morbidity and mortality in cancer survivors (7-11).

[figure not shown]
We hypothesize that non-invasive MRI techniques have the potential to accurately characterize the plaque constituents thereby indicating vulnerability of plaque. We intend to utilize 3 point Dixon (3 PD) and ultra short time to echo (UTE) MRI techniques to identify and measure plaque components such as hemorrhage, necrotic core and fibrous cap in carotid arteries. We intend to conduct an initial baseline MRI, blood tests (to correlate with surrogate markers of inflammation) and other tests whenever available of cardiac or vascular dysfunction (echocardiography and computerized tomography studies). This cohort will be followed up with medication and/or life style modification regimen for a period of initially 18 months and subsequently at 36 months. A repeat of all baseline studies (MRI and blood tests) would be performed as part of the 18 and 36-month follow-up.

We believe these studies would help in identifying the vulnerable plaque features in HNXRT patients and would provide us with a novel opportunity to identify and treat the disease early and hence in long run would reduce health related complications and health care costs.

### **Introduction:**

Radiation therapy (XRT) is critical for the treatment of many benign and malignant neoplasms. It is well established that cancer survivors who have undergone XRT exhibit a long-term survival rate that significantly lags behind age and gender-matched population controls (7-11). Several scientific studies and publications have demonstrated that, of all etiologies of non-cancer mortality, cardiovascular disease (CVD) remains the most significant cause of morbidity and mortality in cancer survivors (7-11). Until recently radiation vasculopathy has attracted little research attention, because patients would often succumb to their malignancy before the vascular conditions manifested clinically (8). This is no longer the rule as more patients are now "outliving" their malignancies and are presenting with the long-term sequelae of cancer treatments (9). Sequelae and manifestations of accelerated atherosclerosis have been identified in the vasculature of almost every organ system (12-15). Atherosclerotic plaques that are susceptible to rupture, termed "vulnerable" or "unstable" consist of a large necrotic core made substantially of lipids and cell debris and a thin, collagen-poor fibrous cap (3, 16-18). Another characteristic of unstable plaques is that they contain numerous inflammatory cells. It has been documented that inflamed plaque and those with a large lipid core and thin fibrous cap are more likely to progress and cause clinical events than those without these features (19-21). Inflammation plays a major role in the onset, progression and destabilization of arterial plaque (22-27). Fig 1. Shows a brief overview of pathobiology and progression of arterial atherosclerosis.

Fig 1: Overview of pathobiology and progression of arterial atherosclerosis

Therefore imaging the vasculature for both its inflammatory state and presence of type of disease is very important (28-30). The potential of magnetic resonance imaging (MRI) to characterize arterial plaques has been extensively studied (1, 31-33). MRI due to its ability of tissue characterization, superior resolution, lack of radiation, non invasiveness is an ideal modality for *in vivo* study of arterial plaques.

There are no studies performed to date that have evaluated MRI arterial plaque characteristics in HNXRT and correlated with serum markers of inflammation, metabolomics, echocardiographic cardiac dysfunction assessment and computerized tomography (CT) coronary calcium scores. Furthermore, no studies have been performed to look into associations between plaque contrast kinetics and morphology using anatomical MRI before and after initiation of medical and-/or life style modification therapy.

## Aims

The purpose of this study is to assess carotid artery MRI plaque characteristics in 100 asymptomatic cancer survivors with history of chest, head and neck radiotherapy (HNXRT) and with subclinical atherosclerosis. Another objective is to analyze plaque changes in the same group after initiation of medical treatment for 18 and 36 months.

The following specific aims (A), research questions (RQ) and hypotheses (H) will be addressed.

A 1: To characterize the plaque constituents including fibrous cap (FC), lipid core and hemorrhage within the carotid plaque by MRI

RQ 1a: What are the predominant plaque constituents?

RQ 1b: Is there a predominance of complex and vulnerable plaque features in the neck arterial vasculature of cancer survivors?

H 1: We hypothesize that there is a predominance of vulnerable plaque in carotid arterial vasculature of HNXRT patients due to the phenomenon of radiation vasculopathy.

A 2: Determine the correlation between plaque inflammation (direct measure by MRI) with serum markers of inflammation through blood tests (hsCRP, LpPLA2, IL-6) and metabolomics

and other tests of cardiac or vascular dysfunction (echocardiography and computerized tomography coronary calcium score studies).

RQ 2: Is there any correlation between the direct and surrogate markers of inflammation?

H 2: We hypothesize that there is a predictable correlation between the direct and surrogate measures of inflammation.

A 3: To assess the longitudinal change in the artery plaque characteristics (inflammation and morphology) with treatment.

RQ 3: Is there a predictable relationship between inflammation (pattern of enhancement-contrast kinetics) and vulnerable features within a plaque?

H 3: We hypothesize that changes in plaque characteristics pre and post treatment would correlate with contrast agent dynamics over time.

A 4: To determine the efficacy of comprehensive treatment (life style modification + statin) versus (life style modification + placebo).

RQ 4: Is one regimen better than the other in cancer survivors with subclinical atherosclerosis?

H 4: We hypothesize that comprehensive treatment (life style modification + statin) would have better inflammation control and favorable plaque modification than life style modification alone as measured by parameters in (A2 & A3).

### **Research Strategy:**

### **Subjects:**

We intend to recruit 100 asymptomatic cancer survivors who had prior history of chest, head and neck radiotherapy (HNXRT). Our potential participants are patients of The Winship Cancer Institute who are being invited to return to The Survivorship Clinic as part of an ongoing funded trial at Emory Survivorship clinic (Novel testing for subclinical cardiovascular disease in lymphoma survivors, IRB 00057029).

### **Inclusion criterion:**

Age 22 and above with prior head and neck or chest irradiation, six months or more post head and neck irradiation, documented subclinical cardiovascular disease (inflammatory markers in the serum, pre-existing plaques [detected by ultrasound, CT or MRI], asymptomatic major arterial stenosis, and not being considered for arterial surgery or endovascular treatment.

### **Exclusion criterion:**

Recurrence of cancer (with or without treatment), planned surgical or endovascular intervention for revascularization of carotid arteries at the time of enrollment, renal failure, eGFR < 45 (calculation based on serum creatinine levels, race, age and gender), medically unstable or hematologic, renal, or hepatic dysfunction, non-atherosclerotic arterial stenosis (dissection), presence of stents or external clips that can cause artifacts impairing accurate interpretation of MRI data, contraindications to MRI: cardiac pacemaker, metal implants, metal in eyes, pregnant

or nursing women, claustrophobia, allergy to MRI contrast; physical or mental impairment that would limit the patient's ability to comply with the medical instructions or study procedures.

### **Setting:**

The research will be coordinated through the Emory School of Medicine, Department of Radiology in partnership with The Winship Cancer Institute, Survivorship Clinic, Department of Cardiology and The Stroke Center. All the aspects of clinical and research assessment and follow-up will be provided within The Emory Healthcare System.

### **Health Evaluation of Patients:**

Antecedents and Screening: Demographic/clinical variables assessed include age, gender, marital status, education, ethnicity, occupation, type of lymphoma, chemotherapy agents used and dosage, and total RT dosage. During screening, the short BLESSED cognitive screening tool (BOMC) is used to exclude those with scores  $> 11$  indicating cognitive impairment that would interfere with participation. The Shortened WHO Rose Angina Questionnaire (Rose) will

be utilized to screen for the presence of unrecognized coronary artery disease. This shortened screening questionnaire includes the three most predictive questions of angina, major coronary events, and coronary heart disease mortality. Assessment of patient heart disease knowledge will be made with the coronary heart disease (CHD) Knowledge Test, a 40 item multiple-choice instrument originally designed to assess self-care, risk factor management, and general knowledge of CHD. Scores are obtained by giving 1 point for each correct answer with higher scores indicating higher knowledge. Health evaluation and tests are conducted as part of 'The Novel Testing for Subclinical Cardiovascular Disease in Lymphoma Survivors' (ongoing funded trial at Emory Survivorship clinic, IRB 00057029).

#### **Variables and Measures:**

Blood will be drawn for testing in the MRI Research Laboratory at EMORY by a research nurse. The blood specimens will be drawn immediately before each MRI examination to measure routine laboratory testing of serum markers of inflammation (hsCRP, LpPLA2, IL-6) and metabolomics. Creatinine will be measured to calculate eGFR. In addition, the Framingham Risk Assessment Tool for General Cardiovascular Disease (FRAT) will be employed to determine the 10-year risk prediction for general cardiovascular events using the assessed values of age; history of diabetes, smoking, and hypertension; systolic blood pressure; and measured total and HDL cholesterol levels.

#### **Other tests:**

[figure not shown]
The following novel markers that will be assessed include measurement of serum levels of BNP, HS-CRP, and cTnI, Echocardiography for the assessment of systolic and diastolic function and structural defects, the presence of coronary artery calcium (CAC) and calcium score with the CT. For all cancer survivors with HNXRT, the above tests (except hsCRP, LpPLA2, IL-6 and metabolomics) will be conducted as part of 'The Novel testing for subclinical cardiovascular disease in lymphoma survivors' (ongoing funded trial at Emory Survivorship clinic, IRB 00057029). We intend to apply for a grant / fund to cover for tests not covered by ongoing funded trial at Emory Survivorship clinic, IRB 00057029.

#### **Examination Plan Overview:**

All participants will be given IRB approved informed consent. Those who decide to take part and give consent for the study would be enrolled in the research study. We would be taking snap shots with MRI at three data points and monitor treatment effects. Overview of the research study is shown in Fig 2. A baseline MRI will be performed to assess arterial atherosclerotic constituents. Once the initial MRI has been performed, and in the case where subclinical disease is present i.e. elevated blood markers or arterial plaque on MRI. HNXRT cancer survivor patient with abnormal tests will be started on treatment, which includes life style modification and-/or lipid lowering medication. Patients with positive tests would be divided randomly into two groups; one group will receive life style modification + statin therapy and the second group will receive life style modification alone. A repeat MRI and blood tests (2nd study) will be performed at 18 months after initiation of such treatment to assess changes in plaque morphology and enhancement characteristics. MRI findings of baseline and final would be

correlated with surrogate markers of inflammation, Echo and CT findings. A final set of MRI and blood tests will be performed at 36 months after initiation of such treatment to assess changes in plaque morphology and enhancement characteristics. MRI findings of baseline and final would be correlated with surrogate markers of inflammation, Echo and CT findings.

Fig 2. Shows overview of the research study

#### Treatment and Clinical Follow-Up:

Patients enrolled in the “Accelerated Atherosclerosis in High Risk Population Groups: An Assessment by Magnetic Resonance Imaging” study will be evaluated in the cardiology clinic by [name],

FACC, FSCAI who is the Director of Peripheral Vascular Intervention at Emory University and treats patients with carotid artery disease. All these patients will be randomized based on the last digit of their medical record number. If the last digit will be an even number they will then be given a statin, which they will take and will also be instructed about regular exercise. Patients will be made aware of the side effects of statins and about the procedures to report these side effects. Patients with the last digit being an odd number will ONLY be advised about exercise. All patients will have regular visits and patients on a statin will be followed up and evaluated for any adverse effects of the medication and for compliance at 18 and 36 months by the study preventive cardiologist. The preventive cardiologist or any other physician involved with care of the patient may elect for more frequent follow up as well as modification or discontinuation of the study prescribed therapy if deemed necessary based on his or her best clinical judgment.

These patients will get routine clinical follow-up in the oncology (The Winship Cancer Institute Clinics) and cardiology clinics (Emory Hospital) as part of the ongoing routine clinical care.

Within five weeks of initial MRI evaluation, our recruited research that demonstrate increased blood markers and/or atherosclerosis on MRI would be subjected to life style modification ± medical (statin) therapy. Department of Cardiology would prescribe and monitor statin therapy: Rosuva (20 mg once a day) with target LDL goal < 70; non-HDL goal < 100 and Aspirin (81 mg once a day). The rational for using rosuva 20 mg is because this dosage has already been successfully used in JUPITER Trial (35). The follow-up by Cardiology department would comprise educating the patients on life style modification and also how to monitor and report any adverse drug affects which if expected would be further assessed with laboratory testing with LFT's and CBC. Any patients who suffer clinical side effects of treatment as part of our research would be taken off our study. Patients will continue to follow-up in the survivorship clinic and with the preventative cardiologist as indicated.

The randomized therapy may be modified or discontinued at the discretion of any physician involved with a study patients' care or the study-designated preventative cardiologist based on clinical judgment. This may occur during scheduled follow up with the study-designated preventative cardiologist or at any point.

Life style modification will be tailored, implemented and followed up by Emory HeartWiseSM Risk Reduction Program. This Program will use several analytical tools including questionnaire (BOMC, Rose, FRAT, CHD Knowledge Test). These analytical tools, laboratory as well as imaging tests will help EmoryHeartWise Risk reduction Program devise the best life style modification and exercise strategy for our patients.

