Statistical analysis: The three parameters mentioned above (Ktrans,  $\square_p$ , vessel wall) continuous variables. Before performing the statistical modeling we will check first to see if the distributions of these variables are normal; otherwise, we will use log transformation prior to the modeling of these parameters. We will first compute the mean, median, and standard deviation at each time point for these parameters. We will plot these data by patient over the 3 time points to examine the longitudinal profiles. We will use the linear mixed effects model (random coefficient model with random intercept and slope) with these parameters serving as dependent variables. The independent variables will be the time indicator and other potential confounders that we may need to control (e.g. age, gender, race, and body mass index). The interest in this model is the coefficient associated with the time indicator, which allows us to obtain the adjusted population mean estimate of these parameters at each of these time points. Since we have the best linear unbiased prediction estimates of the random intercepts and slopes for each subject,

we will be able to examine individual subject profiles and assess the temporal trend for each subject. Thus this random coefficient linear mixed effects model will allow us to obtain the overall adjusted mean estimate ( $K_{trans}$ ),

for each of the individual subjects, overall across all above mentioned time points, and at each of the time points.

To assess the association between the vessel wall area, and  $K_{trans}$  and

linear mixed effects models (random coefficient models) to obtain the estimates of fixed effects.

We will carry out 2 analyses in these models, we will use vessel wall area as the dependent variable and  $K_{trans}$  and

potential confounders if necessary. The slope estimate from these models is interpreted as a measure of adjusted association between the changes in plaque size and morphology, and DCE-MRI dynamic enhancement parameters.

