#### Expected results:

We anticipate that the  $K_{trans}$  and

the size of the plaques (vessel wall area) will change in a favorable way over the time course of the study due to institution of treatment (medicines and life style modification). We anticipate that changes in the vessel wall (plaque and vessel wall remodeling) as measured by high-resolution MRI will change in a way that is predicted by the change in the DCE-MRI inflammation parameters but that changes in the DCE-MRI inflammation parameters will precede those of the morphological changes. We expect this because previous studies have shown changes in inflammatory cell content occur within three months of the initiation of statin therapy, whereas changes in plaque morphology as measured by high-resolution anatomical

MRI occur at approximately twelve to eighteen months following the initiation of statin therapy (19, 41, 42).

A # 2: To investigate the relation between direct measures of plaque inflammation (MRI) and indirect measures of inflammation (blood serum markers of inflammation, Echocardiographic and CT studies) as therapy progresses.

Rationale: DCE-MRI studies have shown a correlation between the number of macrophages and amount of neovasculature and the patterns of dynamic contrast enhancement (42, 43). Our hypothesis is that over a longer period of time (36 months); there would be a correlation between these two (direct and indirect measures of inflammation).

Data analysis: The DCE-MRI dynamic enhancement parameters (Ktrans and  $\square_p$ ) will be determined as described in section SA # 3 above. Samples will be drawn for serum markers of inflammation (hsCRP, LpPLA2, IL-6). Relationship if any between the inflammation within the plaque and serum markers will be observed.

Expected results: We expect a predictable correlation between the inflammatory markers in the blood and inflammation present within the vessel wall/plaque seen on the initial and post treatment sampling; this expectation is based on prior literature (19, 22, 46, 47).

We will carry out the modeling using SAS/STAT procedure MIXED.

A # 4: To determine the efficacy of comprehensive treatment (life style modification + statin) versus life style modification alone.

Rationale: The effects and efficacy of various combinations of treatment have not been studied in the context of radiation vasculopathy and accelerated atherosclerosis.

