#### Project Timeline:

The equipment and resources are currently in place to begin patient examinations immediately upon receiving funding. We anticipate the recruitment of all 100 patients from the existing pool of patients at the Emory Clinics (Survivorship Clinic) within the 12 months of funding. The time from baseline MRI and initial follow-up MRI study will be 18 months which would give us time to observe therapy related changes in the plaque morphology and inflammation, observe correlation between plaque inflammation and inflammatory markers in the serum and also with

cardiac functional status as assessed by echocardiography and CT. The 2nd set of follow up MRI and blood tests at 36 months would serve as the end point for final analyses of the long term effects of the instituted treatment regimen. Thus, if the co-investigators responsible for statistical models receive the complete data 3 months after the end of the studies, it is expected to take another 3 months to complete the entire work. So realistically the project should be completed in 39 months.

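### The statin is allocated by odd or even medical record number, a foreseeable and unconcealed rule that the protocol calls random, so the Aim 4 comparison between arms is open to selection bias

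*Combined protocol and SAP*

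**What the plan says.** The Examination Plan Overview presents the allocation as random: "Patients with positive tests would be divided randomly into two groups", one to receive lifestyle modification with a statin and the other lifestyle modification only. The mechanism appears under Treatment and Clinical Follow-Up: "All these patients will be randomized based on the last digit of their medical record number". Even digits receive the statin and exercise instruction; odd digits receive exercise advice only. The same section later refers to the assigned treatment as randomised.

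On the source of patients, the Subjects section says: "Our potential participants are patients of The Winship Cancer Institute who are being invited to return to The Survivorship Clinic". The Project Timeline expects "recruitment of all 100 patients from the existing pool of patients at the Emory Clinics".

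The exclusion criteria include "medically unstable or hematologic, renal, or hepatic dysfunction". The covariates named for the mixed models are introduced as examples: "e.g. age, gender, race, and body mass index".

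The comparator is worded in two ways. In the Aims section, Aim 4 compares the statin regimen "versus (life style modification + placebo"; the A # 4 entry in the later account of the specific aims has "versus life style modification alone".

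**The concern.** A valid random allocation needs an unpredictable sequence, and the people who recruit and assess eligibility must not know the next assignment. The last digit of an existing record number meets neither condition. Anyone who can see the number knows the arm, and a patient drawn from an existing clinic pool can be taken to have the number before being approached.

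Staff cannot change a patient's digit. They can, knowingly or not, decide differently by arm whom to invite, whom to exclude, and whether a borderline test counts as positive. The two arms may then differ in prognosis before treatment starts, and a difference at 18 or 36 months could not be attributed to the statin with the confidence that randomisation gives.

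Only Aim 4 is at stake. It is, however, the trial's only efficacy comparison between arms, and hypothesis H 4 predicts superiority of the statin regimen.

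**Working it through.** **1. Label against mechanism.** The Examination Plan Overview and Treatment and Clinical Follow-Up use the language of randomisation. The only mechanism given is digit parity. The visible text mentions no generated sequence, central assignment, envelopes, blocking or concealment. Figure 2 is not reproduced and one passage was removed before review, so those could not be checked; the parity rule itself is explicit.

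**2. What is decided while the arm can be known.**
- Invitation and consent: candidates come from the existing clinic pool.
- Exclusions: within the criterion on medical instability and organ dysfunction, only renal function has a numerical cut-off (eGFR below 45). Another exclusion, impairment limiting compliance, is itself partly a judgement of expected adherence.
- Positive tests: the Examination Plan Overview relies on raised blood markers or plaque on MRI, with no threshold for the markers.

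**3. What chance alone does.** If digits are evenly spread, the size of one arm among 100 patients is binomial(100, 0.5), with a 95% range of 40 to 60. Chance imbalance in numbers is modest and is not the problem.

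**4. Illustration of size.** The protocol gives no figure to reproduce, and the inputs on selection and correlation are assumptions. Suppose a fraction p of candidates, those with the worst values on some standard normal factor, is skipped in one arm only. That arm's mean on the factor shifts by d = φ(z₁₋ₚ)/(1 − p):
- p = 10%: 0.1755/0.90 = 0.195
- p = 20%: 0.2800/0.80 = 0.350

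*(a) Selection on the measured baseline value.* With baseline/follow-up correlation ρ and equal variances, the false difference in change is d(1 − ρ). The SD of change is √(2(1 − ρ)). The standardised bias is therefore d√((1 − ρ)/2).

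| ρ | p = 10% | p = 20% |
|---|---|---|
| 0.5 | 0.0975 | 0.175 |
| 0.8 | 0.062 | 0.111 |

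Adjusting for the baseline value removes this bias; in simulation the adjusted difference was zero to within simulation error.

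*(b) Selection on an unmeasured factor.* With correlation r between that factor and the baseline-adjusted outcome, the bias is r·d in SD of the adjusted outcome, and baseline adjustment does not remove it. The Sample Size section plans 100 patients and about 10% attrition: 100 × 0.9 = 90, or 45 per arm if all are allocated and the split is equal. For a two-sided two-sample t test at 0.05, the non-centrality is bias × √(45/2) = bias × 4.743. With no true statin effect:

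| r | p | Bias (SD) | Non-centrality | False-positive rate |
|---|---|---|---|---|
| 0.2 | 10% | 0.039 | 0.185 | 5.4% |
| 0.2 | 20% | 0.070 | 0.332 | 6.2% |
| 0.5 | 10% | 0.0975 | 0.462 | 7.4% |
| 0.5 | 20% | 0.175 | 0.830 | 13.0% |

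The t test stands in for the planned mixed model, so these rates show scale only.

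**5. Comparator wording.** The Aims section specifies placebo. The Examination Plan Overview, Treatment and Clinical Follow-Up and the A # 4 entry describe lifestyle modification without one. This is a separate inconsistency and adds nothing to the case on allocation.

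**The case against.** Several points can fairly be made for the plan.

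- **Parity is unrelated to prognosis, and staff cannot alter it.** True. The objection to the rule is foreknowledge, not the digit.
- **Few decisions are open to influence.** Many exclusions are factual (pacemaker, metal, pregnancy, eGFR), the cognitive screen has a numerical cut-off (score above 11), and documented subclinical disease is already required at entry, so the later positive-test step may remove few patients. The protocol is also unclear whether every enrolled patient is allocated or only those with positive tests. This narrows the room for selection but does not close it: the inclusion criterion gives no marker threshold either, and invitation and the judgement-based exclusions remain.
- **Clinic invitations are made under another trial.** Selective invitation to this study is therefore possible but not shown. That stands; the bias is a risk of the design, not a demonstrated fact.
- **Each patient acts as his or her own control.** The Aim 4 data analysis says this. It covers change within a patient and does not make the two arms comparable.
- **Covariates will deal with it.** The list is optional, is written for Aim 3, and carries over to Aim 4 only through a general reference to earlier techniques. It names neither frailty nor expected adherence.
- **The illustration assumes efficient selection.** It does. If only half of the worst 10–20% are skipped, d falls to 0.092 (0.5 × 0.1755/0.95) or 0.156 (0.5 × 0.2800/0.90), and the false-positive rate in (b) is 5.1% to 6.5%. The numerical effect may be small.
- **Aim 4 does not drive the sample size.** Correct: power is based on Aims 2 and 3. Aim 4 still carries a stated efficacy hypothesis.

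**Conclusion.** The concern holds. Allocation is by a deterministic, foreseeable rule that the protocol calls random, and nothing in the visible text conceals it or offsets the consequence. The defect is confined to Aim 4. The realised bias cannot be derived from the documents. Under the assumed inputs it ranges from negligible to 0.175 SD, with a false-positive rate of up to 13.0% for a nominal 5% test.

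The need for correction does not depend on those figures. It follows from the mechanism: whatever bias occurs, an Aim 4 result obtained under this rule could not properly be described as coming from a randomised comparison. The conclusion assumes that patients in the existing pool already have a record number visible to those who recruit or assess them.

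**What to change.** 1. Replace the parity rule with a computer-generated list, for example permuted blocks of varying size, held by the study statistician or in the study database. Any concealed central sequence would meet the objection.
2. Release each assignment only after consent, baseline MRI, blood results and the positive-test decision have been recorded. State whether all enrolled patients or only those with positive tests are allocated.
3. Flag patients already assigned by parity. Report their baseline characteristics and, as far as records allow, screened and enrolled counts by odd and even digit. Give Aim 4 results with and without them.
4. If most patients are already assigned, describe Aim 4 as quasi-randomised and exploratory, with baseline-adjusted estimates. The protocol is Version 3, dated 2015, and enrolment status is not given, so this may be the only option left.
5. Reconcile the placebo wording in the Aims with the lifestyle-only comparator elsewhere.
6. As a secondary step, give image readers files under a study code without record number, arm or visit order. Contour tracing and the choice of enhancing regions depend on the reader, and no masking is stated. That readers now see the record number is an inference.

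The cost is a protocol amendment, one generated list, a parity tabulation from existing records and recoding of image files. No patients or procedures are added.
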